A unified repeated measures analysis (11,12) will be used to describe the time course and to assess the effects of divergent vs. concave abutment design. This approach will make it possible to take into account the correlation of repeated measures on a given subject over time, and to consider the impact of abutment type, as well as other potential covariates. Subject will be treated as a random effect and other factors as fixed effects. Candidate covariate effects that will be explored include sex, age, history of periodontal disease, tooth position, clinical crown anatomy and the condition of adjacent teeth. So as not to exceed the limitations of sample size, we will first consider the relationship of each candidate with the outcome separately, and incorporate those with promising relationships into subsequent modeling. Parameters will be estimated using restricted maximum likelihood

(REML) methods, and a variety of different variance-covariance structures will be entertained, as appropriate. These approaches can accommodate missing data and possible time-dependency of the covariate, both of which may be relevant to this situation. Appropriateness of assumptions associated with the modeling, such as normality, will be fully assessed, and normalizing transformations considered as appropriate. Should these approaches not appear feasible, nonparametric methods for longitudinal data (13, 14) will be considered.

Comparisons of tissue alterations between the two abutments types at each follow-up time are also of interest: Changes relative to baseline will be compared at each of the four recall time points, initially using either the two-sample Student's t-test to compare abutment types, or its nonparametric analog, the Wilcoxon rank sum test, as appropriate. In addition, standard linear modeling will be used to incorporate the possible impact of other covariates. Adjustment for multiple comparisons will be made using the modified Bonferroni method due to Holm (15) in conjunction with an overall Type I error of 0.05.

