#### POWER CONSIDERATIONS:

Evaluations of power and detectable effect size are calculated for change in peri-implant mucosal zenith position at 12-month follow-up relative to baseline over the course of follow-up. Since this research is to be based on a patient population from another study, sample sizes are fixed at 30 subjects for each of the two abutment groups. Assuming dropout of 10-15% over the year of follow-up, calculations were based on completed sample sizes of 27 and 25 per treatment group. Values of 0.4 – 0.7 mm were found in the literature (18, 19) for the standard deviation (s.d.) of this change measure. Taking a conservative approach, estimates of power and detectable effect size were considered for s.d. values of 0.5, 0.7, 0.9 and 1.0 mm; calculations were made based on a Type I error level ( $\alpha$ ) of 0.05 for the key 12-month comparison, as well as  $\alpha = 0.05/4 = 0.0125$ , representing Bonferroni adjustment for four multiple comparisons corresponding to follow-up evaluations at four time points. Due to the scarcity of information in the literature, standard deviation values were assumed to be uniform across time points. Power was set at 80% and 90% for calculations of detectable effect sizes.

A minimum difference of 1 mm between the two abutment groups was felt to be clinically relevant. Based on these sample sizes, at least 99% power is anticipated to detect this effect size, even with adjustment for multiple comparisons and 15% attrition, if the true standard deviation is within the range found in the literature, i.e., 0.7 mm or less. For a larger standard deviation of 1.0 mm, we anticipate 93% power to detect this difference for a single test, and 82% power with multiple comparisons adjustment, again assuming 15% attrition. We therefore anticipate having more than adequate power to detect a clinically important difference in tissue changes between the two abutment designs. The minimum detectable differences are considerably smaller, as indicated in the table below. These results also show that we will be able to detect, with at least 80% power, differences on the order of that considered clinically relevant even if the standard deviation is somewhat greater than that described in the literature cited.

80% POWER								
Sample Size Per Abutment Group+	Detectable Effect Size Between Abutment Groups (mm)							
	Type I Error Level: $\alpha = 0.05$				Type I Error Level: $\alpha = 0.05/4 = 0.0125^*$			
	SD (mm)				SD (mm)			

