### Average Keratinized Mucosa Width

### Statistical Analyses

We used mixed models to analyze the effect of time and treatment on each of the variables of interest. The results are summarized in tables below.

Canfield values, bleeding on probing, plaque index, gingival index, and keratinized mucosa width changed significantly over time. Canfield values, bleeding on probing, plaque index, and keratinized mucosa width have a curved relationship with time. Treatment alone is not significant in any model, but is significant in

an interaction with time in bucco-lingual thickness; the effect of treatment on this measure is significantly different across time points.

Table 13: Canfield Model

	P-Value
Time	< .001
Time 	< .001
Treatment	0.853

Table 14: Probing Depth Model

	P-Value
Time	0.096
Treatment	0.307

Table 15: Bleeding on Probing Model

	P-Value
Time	0.0791
Time 	0.0282
Treatment	0.9170

Table 16: Plaque Index Model

	P-Value
Time	0.1640
Time 	0.0436
Treatment	0.9880

Table 17: Gingival Index Model

	P-Value
Time	0.00146
Treatment	0.40900

Table 18: Bucco-Lingual Thickness Model

	P-Value
Time	0.0744
Time 	0.1440
Treatment	0.6740
Treatment:Time	0.0169
Treatment:Time 	0.0359

Table 19: Keratinized Mucosa Width Model

	P-Value
Time	< .001
Time 	< .001
Treatment	0.106

Over time, there was not a significant relationship between bucco-lingual thickness and any of Canfield values, probing depth, bleeding on probing, or keratinized mucosa.

Table 20: Canfield and Bucco-Lingual Thickness

	P-Value
Time	< .001
Time 	< .001
Thickness	0.178

Table 21: Probing Depth and Bucco-Lingual Thickness

	P-Value
Time	0.0928
Thickness	0.6720

Table 22: Bleeding on Probing and Bucco-Lingual Thickness

	P-Value
Time	0.1190
Time 	0.0381
Thickness	0.7340

Table 23: Keratinized Mucosa Width and Bucco-Lingual Thickness

	P-Value
Time	< .001
Time 	< .001
Thickness	0.705

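### The adjusted treatment model is chosen by an outcome-driven covariate screen with no cut-off; one pre-stated model with the delivery value as covariate should replace it

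*Combined protocol and SAP*

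**What the plan says.** The protocol's Statistical methods section plans a repeated measures model and lists the covariates: "Candidate covariate effects that will be explored include sex, age, history of periodontal disease, tooth position, clinical crown anatomy and the condition of adjacent teeth". The selection rule follows: "So as not to exceed the limitations of sample size, we will first consider the relationship of each candidate with the outcome separately", and then "incorporate those with promising relationships into subsequent modeling". The section does not define *promising*, does not say whether treatment is in the screening model, and names no covariate that is always kept.

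By-visit comparisons come next: "Changes relative to baseline will be compared at each of the four recall time points, initially using either the two-sample" sample t-test or its rank analogue, without covariates. In addition, "standard linear modeling will be used to incorporate the possible impact of other covariates", again without naming them. Holm's method is applied "in conjunction with an overall Type I error of 0.05". The section does not say whether the adjusted or the unadjusted result is primary. Quantitative secondary outcomes are to be analysed in the same way.

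The 2019 analysis report says: "We used mixed models to analyze the effect of time and treatment on each of the variables of interest". Its treatment models list only time terms, treatment and, for thickness, their interactions. A later section subtracts the delivery value from Canfield, thickness and keratinized width before modelling.

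**The concern.** If covariates are picked by how they relate to the outcome, and the threshold is left open, several adjusted treatment p-values are available and the plan does not say which one counts. Sample size, the reason given, does not force this: two or three covariates chosen in advance fit in about 54 subjects.

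The report raises a second issue. The planned adjustment is absent, and the reader cannot tell whether the screen was run and found nothing or was never run. How baseline is handled also visibly matters. For keratinized width the treatment p-value is 0.106 on raw values (Table 19) and 0.952 after subtraction (Table 29), with delivery means of 3.307 and 2.704. The two models also differ in their time terms, so this is not purely a baseline effect. For thickness the treatment-by-time² p-value moves from 0.0359 (Table 18) to 0.0510 (Table 28). A model fixed beforehand would have settled which of these to report.

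**Working it through.** **1. The plan's own power figures.** These use a two-sided two-sample t-test without covariates, 25 per arm, 48 df and noncentrality δ/(σ√(2/n)). The plan does not state sidedness; two-sided reproduces its figures.

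- δ = 1 mm, σ = 1.0: noncentrality 1/√(2/25) = 3.54. Power is 93.4% at α = 0.05 (stated 93%) and 82.2% at α = 0.0125 (stated 82%).
- δ = 1 mm, σ = 0.7, α = 0.0125: power is 99.2% (stated at least 99%).

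The 0.0125 is described as "representing Bonferroni adjustment for four multiple comparisons corresponding to follow-up evaluations at four time points". All these figures rest on the unadjusted comparison and do not depend on the screen.

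**2. Type I error of the adjusted test.** Simulation with 25 per arm, six independent candidates and 4,000 null trials per scenario (Monte Carlo SE about 0.4 points). The documents give no covariate strengths or cut-offs. Assumed R² patterns: none; two candidates at 0.05; two at 0.15; all six at 0.05.

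| Rule | Type I error at nominal 5% |
|---|---|
| Covariate set fixed in advance | 5.1-5.4% |
| Mechanical screen, each candidate alone, p < 0.10 | 5.1-5.4% |
| Mechanical screen with treatment in the screening model, p < 0.05, 0.10 or 0.20 | 5.9-6.9% |
| Smallest p of six analyses (unadjusted, all six, four screens) | 7.9-10.4% |
| Smallest p over all 64 subsets | 9.8-16.1% |

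The plan's wording fits the second row best. A separate simulation with 29 and 25 subjects gave 6.0-6.3% when only the cut-off was chosen afterwards, and 9.6-11% over all subsets.

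**3. What fixing a set does to power.** Same setup, 1 mm, SD 1.0, α = 0.0125, 5,000 trials per scenario.

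| Assumed strength | Unadjusted | Screened (four rules) | Two fixed | All six fixed |
|---|---|---|---|---|
| None prognostic | 82.3% | 79.7-82.6% | 80.2% | 75.8% |
| Two at R² 0.05 | 82.1% | 81.0-84.9% | 84.6% | 80.4% |
| Two at R² 0.15 | 82.0% | 89.9-92.4% | 93.2% | 90.0% |
| All six at R² 0.05 | 82.4% | 84.9-90.5% | 84.7% | 90.0% |

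The direction depends on which covariates are fixed. Two useless fixed covariates cost 82.3 − 80.2 = about 2 points.

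**4. What the delivery value is worth.** Let B, Y and D be the SDs at delivery, at 12 months and of the change (Tables 1, 11, 12 and 24-26). Then

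cov = (B² + Y² − D²)/2, r = cov/(B·Y), residual variance = Y²(1 − r²), reduction against the change score = 1 − residual/D².

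Example, thickness, divergent arm: cov = (1.1294² + 0.7654² − 1.036²)/2 = 0.394; r = 0.394/(1.1294 × 0.7654) = 0.456; residual = 0.586 × (1 − 0.208) = 0.464; reduction = 1 − 0.464/1.073 = 57%.

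| Outcome, arm | B | Y | D | r | Residual | Against change score | Against raw 12-month value (1 − residual/Y²) |
|---|---|---|---|---|---|---|---|
| Thickness, concave | 1.1291 | 0.5000 | 1.250 | −0.03 | 0.250 | −84% | 0% |
| Thickness, divergent | 1.1294 | 0.7654 | 1.036 | 0.46 | 0.464 | −57% | −21% |
| Keratinized width, concave | 1.8425 | 1.8609 | 1.144 | 0.81 | 1.195 | −9% | −65% |
| Keratinized width, divergent | 1.1373 | 1.0832 | 0.914 | 0.66 | 0.659 | −21% | −44% |
| Canfield, concave | 1.146 | 1.167 | 0.278 | 0.97 | 0.077 | 0% | −94% |
| Canfield, divergent | 1.148 | 1.258 | 0.362 | 0.96 | 0.128 | −3% | −92% |

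Subtraction is close to ideal for Canfield and poor for thickness, where it adds the noise of the delivery measurement. Covariate adjustment is at least as precise as either alternative for all three outcomes. For thickness and keratinized width the delivery SD comes from 31 and 27 subjects and the other two SDs from 29 and 25, so those rows are approximate. A slope common to both arms would give values within or close to these ranges.

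**The case against.** The by-visit tests are first run unadjusted, the power section is built on them, and it treats the 12-month comparison as the key one. None of that passes through the screen. This stands, and it limits the point to the adjusted analyses.

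No harm is visible. The treatment p-values for Canfield are 0.853 (Table 13) and 0.613 (Table 27). From Table 24 the 12-month difference is −0.174 − (−0.238) = 0.064 mm. With a pooled SD of 0.32 mm, its 95% interval is about −0.11 to 0.24 mm, well inside 1 mm. This also stands.

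A reader might infer that the report left covariates out because of what they did to the result, or that its error rate was inflated. The documents support neither: they are silent on whether the screen was run. Nor is it right that the report uses no covariates at all. Tables 20-23 include thickness as a predictor, though without a treatment term.

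A reader might also infer that screening loses power against a fixed set. Step 3 shows that this is not general. The delivery value, which can be a strong predictor, is not among the six candidates, so its benefit comes from adding a covariate and not from abandoning the screen. Nothing in the documents shows that tooth position predicts the outcome.

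Finally, a set chosen now, with results tabulated, is itself post hoc. That is true, and the rerun has to say so.

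**Conclusion.** The point holds as one about specification. The screening rule leaves the adjusted treatment test open, and the report neither applies the rule nor explains its absence. Type I error is about 5% under a mechanical screen of each candidate alone, 6-7% if treatment is in the screening model, and roughly 10% or more only under free choice of subset. These figures rest on assumed covariate strengths and cut-offs.

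The documents' own SDs support adding the delivery value as a covariate. Compared with the change score, the gain in 12-month residual variance is large for thickness (about 57-84%), modest for keratinized width (9-21%) and negligible for the primary Canfield outcome (0-3%). A fixed set gains power only if its covariates are prognostic; otherwise it costs about 2 points for two covariates. Power for 1 mm is at least 99% at an SD of 0.7 mm or less, so the trial's target is not threatened. The reported primary conclusion is not shown to be affected.

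**What to change.** Replace the screening sentence with one pre-stated adjusted model for the quantitative outcomes. It would contain treatment, visit, their interaction and, where it was measured (Canfield, bucco-lingual thickness, keratinized width), the delivery value as a covariate, with only the recall visits as outcomes. Tooth position may be added if its groups are written down beforehand, for example central incisor, lateral incisor, canine and first premolar. State whether this model or the unadjusted comparison is primary. Label models with any other candidate as sensitivity or exploratory analyses.

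Rerun the reported treatment models this way, mark them as post hoc because results are already tabulated, and state whether the planned screen was carried out.

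The cost is a paragraph of SAP wording and one rerun on data already collected. The delivery value uses one degree of freedom and four tooth groups use three. If they prove unimportant, the loss of power is small, on the order of the 2 points above.

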#### POWER CONSIDERATIONS:

Evaluations of power and detectable effect size are calculated for change in peri-implant mucosal zenith position at 12-month follow-up relative to baseline over the course of follow-up. Since this research is to be based on a patient population from another study, sample sizes are fixed at 30 subjects for each of the two abutment groups. Assuming dropout of 10-15% over the year of follow-up, calculations were based on completed sample sizes of 27 and 25 per treatment group. Values of 0.4 – 0.7 mm were found in the literature (18, 19) for the standard deviation (s.d.) of this change measure. Taking a conservative approach, estimates of power and detectable effect size were considered for s.d. values of 0.5, 0.7, 0.9 and 1.0 mm; calculations were made based on a Type I error level ( $\alpha$ ) of 0.05 for the key 12-month comparison, as well as  $\alpha = 0.05/4 = 0.0125$ , representing Bonferroni adjustment for four multiple comparisons corresponding to follow-up evaluations at four time points. Due to the scarcity of information in the literature, standard deviation values were assumed to be uniform across time points. Power was set at 80% and 90% for calculations of detectable effect sizes.

A minimum difference of 1 mm between the two abutment groups was felt to be clinically relevant. Based on these sample sizes, at least 99% power is anticipated to detect this effect size, even with adjustment for multiple comparisons and 15% attrition, if the true standard deviation is within the range found in the literature, i.e., 0.7 mm or less. For a larger standard deviation of 1.0 mm, we anticipate 93% power to detect this difference for a single test, and 82% power with multiple comparisons adjustment, again assuming 15% attrition. We therefore anticipate having more than adequate power to detect a clinically important difference in tissue changes between the two abutment designs. The minimum detectable differences are considerably smaller, as indicated in the table below. These results also show that we will be able to detect, with at least 80% power, differences on the order of that considered clinically relevant even if the standard deviation is somewhat greater than that described in the literature cited.

80% POWER								
Sample Size Per Abutment Group+	Detectable Effect Size Between Abutment Groups (mm)							
	Type I Error Level: $\alpha = 0.05$				Type I Error Level: $\alpha = 0.05/4 = 0.0125^*$			
	SD (mm)				SD (mm)			
25	0.40	0.57	0.73	0.81	0.49	0.68	0.88	0.98
27	0.39	0.54	0.70	0.78	0.47	0.66	0.84	0.94
90% POWER								
Sample Size Per Abutment Group+	Detectable Effect Size Between Abutment Groups (mm)							
	Type I Error Level: $\alpha = 0.05$				Type I Error Level: $\alpha = 0.05/4 = 0.0125^*$			
	SD (mm)				SD (mm)			
25	0.47	0.66	0.84	0.94	0.55	0.77	1.00	1.11
27	0.45	0.63	0.81	0.90	0.53	0.74	0.96	1.06

\*Based upon Bonferroni adjustment for multiple comparisons corresponding to four follow-up times.

+ Based upon recruitment of 30 per group and attrition of 15% (25 per group) or 10% (27 per group)

**Details of products requested**

Product	Ref. No.	Quantity
Osseospeed Plus 3.6 S (H 9.0mm)	25069	12
Osseospeed Plus 3.6 S (H 11.0mm)	25070	12
Osseospeed Plus 3.6 S (H 13.0mm)	25071	6
Osseospeed Plus 4.2 S (H 9.0mm)	25072	12
Osseospeed Plus 4.2 S (H 11.0mm)	25073	12
Osseospeed Plus 4.2 S (H 13.0mm)	25074	6
Osseospeed Plus 4.8 S (H 9.0mm)	25075	5
Osseospeed Plus 4.8 S (H 11.0mm)	25076	5
Osseospeed Plus 4.8 S (H 13.0mm)	25077	5
Healing Abutment 3.6 (4.2mm low)	25128	20
Healing Abutment 3.6 (4.2mm high)	25127	10
Healing Abutment 4.2 (5.0mm low)	25102	20
Healing Abutment 4.2 (5.0mm high)	25103	10

Product	Ref. No.	Quantity
Healing Abutment 4.8 (5.0mm low)	25105	15
Implant Pick-Up 3.6	25130	30
Implant Pick-Up 4.2	25131	30
Implant Pick-Up 4.8	25132	15
Implant Replica 3.6	25133	30
Implant Replica 4.2	25134	30
Implant Replica 4.8	25135	15

# Periimplant Mucosa Dynamics Around Dynamic and Concave AtlantisTM Abutment Transition Profiles

October 1, 2019

We removed all patients without a randomized treatment and/or without any data collection. We did keep subjects with partial data in at least one of the variables. All analyses were performed using R version 3.6.0.

Table 1: Canfield

Treatment	Mean	SD	Min	Max	Median	N
Delivery						
Concave	9.770	1.146	7.46	11.67	9.86	29
Divergent	9.860	1.148	7.42	11.90	10.06	25
1 Month						
Concave	9.618	1.160	7.05	11.52	9.79	29
Divergent	9.684	1.203	7.25	11.92	9.84	25
3 Month						
Concave	9.610	1.174	6.96	11.52	9.75	29
Divergent	9.674	1.231	7.10	11.78	9.81	25
6 Month						
Concave	9.599	1.160	7.10	11.52	9.73	29
Divergent	9.652	1.166	7.27	11.56	9.80	25
12 Month						
Concave	9.596	1.167	6.91	11.45	9.70	29
Divergent	9.622	1.258	6.89	11.54	9.80	25

Average Canfield

[figure not shown]

Table 2: Geomagic

	Mean	SD	Min	Max	Median	N
Ld (Divergent)	2.5039	0.6349	1.4212	4.1078	2.457	29
Lc (Concave)	2.6484	0.6608	1.5736	4.3982	2.539	29
Δ Linear (Lc - Ld)	0.1445	0.1361	0.0122	0.6119	0.117	29
Vd (Divergent)	165.8893	41.7412	91.9577	242.6630	165.796	29
Vc (Concave)	157.9359	41.1081	88.1219	226.8050	161.692	29
Δ Volume (Vc - Vd)	-7.9534	6.1022	-21.7929	-0.2594	-6.537	29

Table 3: Probing Depth

Surface	Treatment	Mean	SD	Min	Max	Median	N
1 Month							
MB	Concave	2.68	0.65	2	4	3	31
	Divergent	2.63	0.56	2	4	3	27
MIDB	Concave	1.5	0.5	1	2	1.5	27
	Divergent	1.82	0.66	1	3	2	22
DB	Concave	2.58	0.72	2	4	2	31
	Divergent	2.85	0.77	2	4	3	27
ML	Concave	2.81	0.7	2	4	3	31
	Divergent	2.85	0.77	1	4	3	27
MIDL	Concave	1.89	0.51	1	3	2	27
	Divergent	1.86	0.77	1	3	2	22
DL	Concave	2.84	0.78	2	5	3	31
	Divergent	2.85	0.82	1	4	3	27
Average	Concave	2.42	0.4	1.67	3.17	2.5	31
	Divergent	2.53	0.45	1.67	3.25	2.5	27
3 Months							
MB	Concave	2.68	0.6	2	4	3	31
	Divergent	2.56	0.58	2	4	3	25
MIDB	Concave	1.63	0.49	1	2	2	27
	Divergent	1.75	0.61	1	3	2	22
DB	Concave	2.58	0.67	2	4	2	31
	Divergent	2.92	0.57	2	4	3	25
ML	Concave	2.84	0.86	1	5	3	31
	Divergent	3.06	0.68	2	4	3	25
MIDL	Concave	1.85	0.77	1	3	2	27
	Divergent	2.18	0.73	1	4	2	22
DL	Concave	2.94	0.73	2	4	3	31
	Divergent	3.12	0.73	2	5	3	25
Average	Concave	2.47	0.47	1.67	3.5	2.5	31
	Divergent	2.61	0.56	1	3.67	2.67	25

Table 4: Probing Depth, continued

Surface	Treatment	Mean	SD	Min	Max	Median	N
6 Months							
MB	Concave	2.82	0.84	2	6	3	30
	Divergent	2.56	0.65	1	4	3	25
MIDB	Concave	1.57	0.57	1	3	2	30
	Divergent	1.78	0.65	1	3	2	25
DB	Concave	2.83	0.65	2	4	3	30
	Divergent	2.68	0.75	1	4	3	25
ML	Concave	2.87	0.78	1	5	3	30
	Divergent	2.92	0.49	2	4	3	25
MIDL	Concave	2.03	0.67	1	3	2	30
	Divergent	2.08	0.57	1	3	2	25
DL	Concave	3	0.83	1	5	3	30
	Divergent	3.08	0.7	2	4	3	25
Average	Concave	2.52	0.46	1.67	3.5	2.5	30
	Divergent	2.52	0.38	1.83	3.17	2.5	25
12 Months							
MB	Concave	2.8	0.72	2	5	3	28
	Divergent	2.76	0.97	2	6	3	25
MIDB	Concave	1.54	0.58	1	3	1.5	28
	Divergent	1.84	0.69	1	4	2	25
DB	Concave	2.89	0.82	2	6	3	28
	Divergent	2.96	0.61	2	4	3	25
ML	Concave	2.96	0.79	2	5	3	28
	Divergent	3.2	0.87	2	5	3	25
MIDL	Concave	2	0.61	1	3	2	28
	Divergent	2.12	0.88	1	5	2	25
DL	Concave	3.11	0.88	2	6	3	28
	Divergent	3.16	0.69	2	5	3	25
Average	Concave	2.55	0.5	1.67	4	2.54	28
	Divergent	2.67	0.54	1.67	4	2.83	25

[figure not shown]

Table 5: Bleeding on Probing

Surface	Time	Concave	Divergent
MB	1 Month	25.81%	29.63%
	3 Months	22.58%	11.11%
	6 Months	19.35%	11.11%
	12 Months	22.58%	18.52%
MIDB	1 Month	25.81%	29.63%
	3 Months	6.452%	25.93%
	6 Months	22.58%	18.52%
	12 Months	29.03%	22.22%
DB	1 Month	9.677%	14.81%
	3 Months	6.452%	22.22%
	6 Months	12.9%	14.81%
	12 Months	25.81%	22.22%
ML	1 Month	25.81%	29.63%
	3 Months	35.48%	22.22%
	6 Months	12.9%	14.81%
	12 Months	19.35%	33.33%
MIDL	1 Month	9.677%	14.81%
	3 Months	12.9%	7.407%
	6 Months	22.58%	14.81%
	12 Months	29.03%	14.81%
DL	1 Month	12.9%	29.63%
	3 Months	19.35%	22.22%
	6 Months	19.35%	25.93%
	12 Months	35.48%	37.04%

